### 17.2 Secondary Endpoints Analysis

#### 17.2.1 Analysis of Long term HRQL outcomes

The main HRQL outcome will be of the overall FACT sum score (FACT-G + FACT-Hep). The main analysis will be a random effects (repeated measures) analysis of the HRQL measures obtained using data taken at baseline, end of treatment, 2 weeks after treatment completion, and every 3 months thereafter (until 24 months). Depending on the amount of missing data at later time points, including for those patients who experience the primary outcome, are transplanted, or are loss to follow-up, the HRQL analysis may be truncated before 24 months (e.g., 12m months). For each patient the model will fit a random intercept and slope term. We will center time to the assessment time point nearest the center of

the time points of the data. Data will be inspected for linearity in time as well as constancy of variances. If the data show deviations from these linearity or constancy of variables we will attempt to remedy this through addition of nonlinearity terms or transformations.

The specific domains of HRQL that are impacted by the different treatments will be analyzed as secondary variables using the same analysis plan as the overall FACT score.

Additionally we will analyze both the primary (overall FACT score) and secondary (domain scores) long term HRQL measures in a descriptive manner both numerically (e.g. means, medians, standard deviations, ranges and interquartile ranges) comparing the groups, testing using analysis of covariance (ANCOVA accounting for baseline values) and graphically by plotting measures using jit plots, spaghetti plots (plots through time where individual patients data from multiple time points are connected with lines) and plots of the means or difference from baseline as estimated from the ANCOVA, or similar plots as suggested by the data. We will examine missing data for systematic bias.

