## 6.0 Health Related Quality of Life (HRQL)

To assess HRQL, subjects will be assessed using the Functional Assessment of Cancer Therapy—Hepatobiliary (FACT-Hep) Questionnaire (Appendix D). This 45-item self-report instrument is designed to measure HRQL in patients with hepatobiliary cancers and is one of the most widely-used instruments in this clinical area. The FACT-Hep consists of the 27-item FACT-G, which assesses generic HRQL, and the 18-item Hepatobiliary Subscale (HS), which assesses disease-specific issues such as pain, appetite, and cramping. The FACT-G is divided into four HRQL domains: physical well-being (7 items), social/family well-being (7 items), emotional well-being (6 items), and functional well-being (7 items). All items have a 7-day reference period and are scored from 0-4 (“not at all” to “very much”), with higher scores indicating better HRQL. Score ranges are 0-28 for physical well-being, 0-28 for social/family well-being, 0-24 for emotional well-being, 0-28 for functional well-being, and 0-72 for HS. All subscale scores from the FACT-G and HS can be summed together to create a total FACT-Hep score, with a possible range of 0-180. The FACT-Hep takes approximately 10 minutes to complete.

Subjects assigned to the SBRT arm will complete the FACT-Hep at baseline/screening, at the time of the second fraction of the SBRT treatment (post treatment prior to discharge), on the last day of treatment (post treatment prior to discharge), 2 weeks after treatment, and at the time of follow-up scans at 3, 6, 9, 12, 15, 18, 21 and 24 months from randomization or until liver transplantation.

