### 13.2 Secondary Variable

To assess HRQL, subjects will be assessed using the Functional Assessment of Cancer Therapy—Hepatobiliary (FACT-Hep) Questionnaire (Appendix D). This 45-item self-report instrument is designed to measure HRQL in patients with hepatobiliary cancers and is one of the most widely-used instruments in this clinical area. The FACT-Hep consists of the 27-item FACT-G, which assesses generic HRQL, and the 18-item Hepatobiliary Subscale (HS), which assesses disease-specific issues such as pain, appetite, and cramping. The FACT-G is divided into four HRQL domains: physical well-being (7 items), social/family well-being (7 items), emotional well-being (6 items), and functional well-being (7 items). All items have a 7-day reference period and are scored from 0-4 (“not at all” to “very much”), with higher scores indicating better HRQL. Score ranges are 0-28 for physical well-being, 0-28 for social/family well-being, 0-24 for emotional well-being, 0-28 for functional well-being, and 0-72 for HS. All subscale scores from the FACT-G and HS can be summed together to create a total FACT-Hep score, with a possible range of 0-180. The FACT-Hep takes approximately 10 minutes to complete.

Subjects assigned to the SBRT arm will complete the FACT-Hep at baseline, at the time of the second fraction of the SBRT treatment, on the last day of treatment, 2 weeks after treatment, and at the time of follow-up scans at 3, 6, 9, 12, 15, 18, 21 and 24 months from randomization or until liver transplantation.

Subjects assigned to the TACE arm will complete the FACT-Hep at baseline, TACE treatment #1, 2 weeks after treatment #1, at TACE treatment #2, 2 weeks after treatment #2, at TACE treatment #3, and 2 weeks after treatment #3. The number of TACE treatments will vary from 1 to 3, so not all HRQL assessments will be collected for all subjects. The HRQL assessment at the time of the last TACE will serve as the HRQL assessment on the last day of treatment, while the HRQL assessment done 2 weeks after the last TACE assessment will serve as the 2 weeks after treatment assessment. HRQL will then continue to be collected at the time of follow up scans at 3, 6, 9, 12, 15, 18, 21 and 24 months from randomization or until transplantation.

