#### 17.2.2 Analysis of Short Term HRQL Outcomes

We will use descriptive statistics (e.g., mean, standard deviation, median, ranges and interquartile ranges) to describe the overall FACT sum score and each domain score by treatment arm at each assessment period from baseline through the end of treatment. We will graph the data over the appropriate time frame similar to the analysis of the long term HRQL measures. This will inform us about the HRQL trajectories during treatment by treatment arm. If the data suggest it is reasonable we will calculate HRQL life years from areas under the curves and compare the treatment arms using ANCOVA or Wilcoxon test, as indicated by the data. We will examine missing data for systematic bias.

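### Section 17.2.1 writes the main quality-of-life score as FACT-G + FACT-Hep, although FACT-Hep as defined in sections 6.0 and 13.2 already contains FACT-G: a minor correction to a secondary outcome's formula

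*Combined protocol and SAP*

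**What the plan says.** The protocol describes the instrument twice, in sections 6.0 and 13.2, in matching terms. Section 6.0 gives its length: "This 45-item self-report instrument is designed to measure HRQL in patients with hepatobiliary cancers". Section 13.2 gives its composition: "The FACT-Hep consists of the 27-item FACT-G, which assesses generic HRQL, and the 18-item Hepatobiliary Subscale (HS"). Section 6.0 splits FACT-G into four domains, "physical well-being (7 items), social/family well-being (7 items), emotional well-being (6 items), and functional well-being (7 items"). Both sections give a score range for each part; those listed last are "0-24 for emotional well-being, 0-28 for functional well-being, and 0-72 for HS". Section 6.0 then says that all the parts can be "summed together to create a total FACT-Hep score, with a possible range of 0-180", and section 13.2 repeats this.

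The analysis section uses a different formula. Section 17.2.1 states: "The main HRQL outcome will be of the overall FACT sum score (FACT-G + FACT-Hep"). It calls this overall score the primary one among the long-term measures and plans to analyse "both the primary (overall FACT score) and secondary (domain scores) long term HRQL measures" descriptively and by ANCOVA, in addition to the random-effects model. Section 17.2.2 uses the same term without redefining it, planning to "describe the overall FACT sum score and each domain score by treatment arm at each assessment period".

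**The concern.** The plan fixes the meaning of its terms and then departs from them in the one formula that an analyst would program. Sections 6.0 and 13.2 keep the name FACT-Hep for the whole 45-item instrument and call the 18 disease-specific items the Hepatobiliary Subscale, or HS. The questionnaire in Appendix D, titled FACT-Hep, also contains the four FACT-G sections. Nowhere does FACT-Hep mean the 18 items alone. Adding FACT-G to FACT-Hep therefore adds FACT-G to a total that already includes it.

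Quality of life is listed first among the secondary objectives and endpoints, and section 17.2.1 makes this score the outcome of its main model. Two programmers could produce two different scores from the same responses, one following the formula and one following the definition. The score as written would give the generic items double weight relative to the disease-specific ones, and its values could not be read against the 0 to 180 range that the plan states. Because the trial is open-label (section 15.0), it is better to settle the definition before results by arm are examined.

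**Working it through.** **Inputs**, all from sections 6.0 and 13.2: every item is scored 0 to 4; FACT-G domains have 7, 7, 6 and 7 items with maxima 28, 28, 24 and 28; HS has 18 items with maximum 72; the stated total is 45 items, 0 to 180.

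**Step 1. Reproduce the plan's own figure.**
- FACT-G items: 7 + 7 + 6 + 7 = 27. Adding HS: 27 + 18 = 45, as stated.
- FACT-G maximum: 28 + 28 + 24 + 28 = 108. Adding HS: 108 + 72 = 180, as stated.

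The definition in sections 6.0 and 13.2 is internally consistent.

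**Step 2. Apply the formula in section 17.2.1 literally.**
- FACT-G + FACT-Hep = FACT-G + (FACT-G + HS) = 2 × FACT-G + HS.
- Maximum: 108 + 180 = 288.

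**Step 3. Compare the weights.**

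| Share of maximum points | FACT-Hep total | Formula as written |
|---|---|---|
| FACT-G | 108/180 = 60% | 216/288 = 75% |
| HS | 72/180 = 40% | 72/288 = 25% |

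**Step 4. Effect on a difference between arms.** Let the arms differ by dG points on FACT-G and dH points on HS.
- FACT-Hep total: dG + dH.
- Formula as written: 2dG + dH.
- Discrepancy: (2dG + dH) − (dG + dH) = dG.

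So a difference confined to FACT-G doubles in points. A difference confined to HS is the same in points but sits on a score whose range is 288 rather than 180. The two scores agree in raw points only when dG = 0. A difference in proportion to the maxima is no exception: with dG = 108k and dH = 72k, the results are 180k and 288k.

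**Step 5. What cannot be computed.** The effect on a test or a confidence interval depends on the standard deviations of FACT-G and HS and on their correlation. The documents give none of these.

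For illustration only, assume standard deviations proportional to the maxima (108:72 = 3:2) and a FACT-G/HS correlation r between 0 and 0.7. Moving from the FACT-Hep total to the formula as written changes the standard deviation from √(9 + 4 + 12r) to √(36 + 4 + 24r), in common units. The ratio of the first to the second is √(13/40) = 0.57 at r = 0 and √(21.4/56.8) = 0.61 at r = 0.7. The standardised difference is then multiplied by:
- 0.57 to 0.61 for a difference confined to HS (points unchanged);
- 0.91 to 0.98 for a difference proportional to the maxima (points multiplied by 288/180 = 1.6).

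These figures show only that the choice of score can matter; they are not estimates for this trial.

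**The case against.** The best answer is that nobody would build the 0 to 288 score. The plan defines exactly one total, the FACT-Hep score of 0 to 180, and the overall sum score in section 17.2.1 maps naturally onto it. Sections 17.2.1 and 17.2.2 contrast one overall score with its domain scores, which fits that total. No section gives a range of 0 to 288, a doubled weight or a reason for one. This stands, and it is why the point is minor. It does not remove the conflict: the intended reading has to be inferred against the plan's own use of the name.

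A second answer is that the two candidate scores are nearly the same variable. If FACT-G and HS are not negatively correlated (an assumption), their correlation is at least 2√2/3 = 0.94, whatever the ratio of standard deviations. With zero correlation and x the ratio of the FACT-G variance to the HS variance, it equals (2x + 1)/√((x + 1)(4x + 1)), which is smallest at x = 0.5, and a positive correlation only raises it. Conclusions would therefore often agree. This too stands, but a difference confined to HS could still be noticeably diluted, as the illustration in the working shows.

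A third answer is that the domains are analysed separately by the same methods, so their results do not depend on the formula. That is correct for the four FACT-G domains. It covers HS only if HS is counted as a domain, which the plan does not say expressly.

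A reader might also infer more than the documents support:
- That the plan deliberately double-weights generic quality of life. Nothing in the text says so.
- That effects on HS shrink by 37.5% and effects on FACT-G grow by 25%. Those figures follow only if differences are expressed as a share of scale range: (1/288)/(1/180) = 0.625 and (2/288)/(1/180) = 1.25. The plan analyses the score itself, where the HS difference is unchanged in points and the FACT-G difference doubles.
- That power is lost by a known amount. No input for such a figure is given.

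**Conclusion.** The inconsistency is real, and the formula in section 17.2.1 is wrong as written under the plan's own definitions. Taken literally it gives 2 × FACT-G + HS on a range of 0 to 288 instead of 0 to 180, with the shift in weights shown above. The arithmetic rests only on the item counts and ranges in sections 6.0 and 13.2; the size of any effect on inference is unknown.

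It is probably a labelling slip, with FACT-Hep written where HS was meant. Its reach is the overall score of one secondary endpoint in section 17.2.1 and the reuse of that term in section 17.2.2. The domain scores, the primary analysis of time to residual or recurrent disease, and the sample size do not depend on it. It is a minor correction, not a dispute about method and not a threat to the trial's main conclusion.

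**What to change.** In section 17.2.1, replace the bracketed formula after the name of the main outcome with: (FACT-Hep total = FACT-G + Hepatobiliary Subscale, range 0-180). This adopts the definition already in sections 6.0 and 13.2. Section 17.2.2 takes its term from section 17.2.1 and needs no separate edit.

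The cost is one phrase. No new data are needed, since the total is computed from item responses already being collected, and neither the model nor the sample size changes.

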If there is a radiological discrepancy regarding findings of residual, recurrent or progressive disease, the site must submit the subject's de-identified images to the centralized radiology panel overseen at LHMC. The panel will make the final determination and notify the site investigator. Any additional ablative treatment, be it to repeat TACE or SBRT or other therapy will be determined at that time. All treatment will be individualized by subject at the discretion of the transplant team.

5.6 Additional local treatment to the target lesion(s) in the assigned treatment arm:

Group 1: SBRT (Arm A), subjects with residual disease or local recurrence ***in the previously treated lesion(s)*** on radiologic imaging at any point in follow up will be considered as having met the primary endpoint of the trial and they are off the study. Patients may be considered candidates for additional local regional therapy to the treated lesion of any kind per the discretion of the treating.

Group 2: TACE (Arm B), subjects with residual disease or local recurrence ***in the previously treated lesion(s)*** on radiologic imaging at any point in follow up will be considered as having met the primary endpoint of the trial and they are off the study. Patients may be considered candidates for additional local regional therapy to the treated lesion(s) of any kind per the discretion of the treating providers.

5.7 Patients in either group who develop new ***intrahepatic lesion(s)*** at any point in follow up will ***not have met the primary endpoint as they have not progressed at the site of previous treatment.*** They may be considered candidates for additional local regional therapy to the new site of disease ***of any kind*** per the discretion of the treating providers and will be followed per Table 4 thereafter.

5.8 If patients have no evidence of progression or residual disease in the treated lesion(s) ***but develop new tumors outside the previously treated field*** and, per the discretion of the treating providers, require treatment with systemic therapy, the patient will be censored from the data analysis for the primary endpoint and will be discontinued from the study.

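### The main HRQL model takes baseline as one more outcome rather than adjusting for it, so an arm difference read at the centred time gains almost no precision from baseline

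*Combined protocol and SAP*

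**What the plan says.** Section 17.2.1 describes the main analysis of the overall FACT score as a "random effects (repeated measures) analysis of the HRQL measures obtained using data taken at baseline, end of treatment, 2 weeks after treatment completion", followed by three-monthly data to month 24. On its form it says "For each patient the model will fit a random intercept and slope term", and on the time scale "We will center time to the assessment time point nearest the center of" the observed time points. Linearity and constant variance will be inspected; if they fail, "we will attempt to remedy this through addition of nonlinearity terms or transformations". Depending on missing data, "the HRQL analysis may be truncated before 24 months (e.g., 12m months".

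Baseline adjustment appears once, among analyses introduced as additional and descriptive: "testing using analysis of covariance (ANCOVA accounting for baseline values". The section does not list the fixed effects, say whether the arms share a baseline mean, or name the treatment contrast to be tested. Domain scores follow the same plan, and section 17.2.3 carries the HRQL approach over to other quantitative secondary outcomes.

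Section 6.0 sets the schedule: baseline, assessments around treatment, then "at the time of follow-up scans at 3, 6, 9, 12, 15, 18, 21 and 24 months from randomization or until liver transplantation". Under item 5.6, patients with residual or recurrent disease in a treated lesion "will be considered as having met the primary endpoint of the trial and they are off the study", so HRQL collection thins quickly.

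**The concern.** Baseline FACT-Hep is collected at screening, before randomization, so the true arm difference there is zero. A model that includes baseline among the responses but lets each arm have its own line ignores that fact. There are two consequences if the treatment effect is the difference in level at the centred time:

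- Baseline is used as another noisy outcome, so it does not remove between-patient variance from the comparison.
- A line drawn through a point with no effect and later points with an effect misstates the difference. How far, and in which direction, depends on where time is centred and who remains.

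HRQL is the first-listed secondary endpoint, and the background section gives possibly better preserved quality of life as part of the case for SBRT. Precision lost here is lost on a comparison that readers will look for.

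**Working it through.** **1. The plan's own figures.** The documents give no HRQL SD, correlation, effect or power. The nearest check is the primary endpoint: 4(1.960 + 0.842)²/(ln 0.6)² = 31.4/0.261 = 120 events (plan: 120), and 134/0.6 = 223 days (plan: 223). I therefore take 98 per arm, medians of 134 and 223 days and 15% yearly dropout (section 16.0 and Table 7) as inputs.

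**2. Where the centre falls.** The schedule has 11 points: baseline, end of treatment, 2 weeks later, and months 3 to 24. The middle point is month 9, the middle of the range is month 12, and the data-weighted middle is about month 3. If cut at month 12, the middle point is month 3 and the middle of the range is month 6.

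**3. Closed-form check.** Assume equal correlation ρ between visits, no attrition, and a constant difference of 0.3 SD at the 10 post-baseline visits.

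- Baseline as an eleventh outcome, arm as a main effect: estimate 0.3 × 10/11 = 0.273; variance (2/98)[ρ + (1−ρ)/11].
- ANCOVA on the post-baseline mean: estimate 0.3; variance (2/98)[ρ + (1−ρ)/10 − ρ²].

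| ρ | Baseline as outcome: SE, power | ANCOVA: SE, power |
|---|---|---|
| 0.5 | 0.106, 73% | 0.078, 97% |
| 0.7 | 0.122, 61% | 0.070, 99% |

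**4. Random intercept and slope, no attrition.** Generalised least squares (GLS) on the protocol's visit times, slope SD 0.01 SD per month, arm difference at the centred time:

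| Correlation | SE, baseline as response | SE, baseline dropped | SE, baseline constrained equal |
|---|---|---|---|
| 0.5 | 0.107 | 0.107 | 0.080 |
| 0.7 | 0.123 | 0.123 | 0.071 |

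Including baseline as a free response gives the same SE as leaving it out. In patient numbers, (0.107/0.080)² = 1.8 and (0.123/0.071)² = 3.0.

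**5. Expected numbers on study at month 9 (274 days).** TACE: 98 × 0.5^(274/134) × 0.85^0.75 = 98 × 0.242 × 0.885 = 21. SBRT: 98 × 0.5^(274/223) × 0.885 = 37. Section 16.0 believes that more than 50% are transplanted within 2 years. A constant hazard giving 50% at 24 months multiplies both by 0.5^(9/24) = 0.771, leaving 16 and 29.

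**6. GLS with attrition.** Assumptions not in the documents: SD 20, intraclass correlation 0.5–0.7, slope SD 0.5 per month, a difference of 0 at baseline and 6 points afterwards, end of treatment at month 1, everyone retained to 1.5 months, and the transplant hazard of step 5. The plan's model is taken to have arm, time and arm-by-time terms. The like-for-like comparator has one common baseline mean, then a post-treatment step and linear trend by arm. Power is Φ(estimate/SE − 1.96).

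| Contrast at | Plan's model: estimate | SE | Power | Baseline-constrained power |
|---|---|---|---|---|
| Month 3 | 4.73–4.76 | 2.30–2.55 | 46–54% | 90–96% |
| Month 9 | 6.2–6.4 | 3.26–3.32 | 47–50% | 51–63% |

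The constrained model at month 3 estimates 6.0 with SE 1.62–1.87. Example at correlation 0.7: Φ(4.76/2.55 − 1.96) = Φ(−0.09) = 46% against Φ(6/1.62 − 1.96) = Φ(1.74) = 96%. Bias at month 3 is 1 − 4.73/6 = 21%. At month 9 the estimate is 5.9–6.4 across the two retention assumptions; centred at month 12 it reaches as much as 7.2.

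**7. Slope as the tested contrast.** If the arms diverge linearly, the unconstrained model keeps 93–99% of the baseline-constrained z (for example 10.41/10.96 = 95%). If instead the difference is the constant step of item 6, the slope test has 11–16% power.

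**The case against.** The strongest reply is that the section does not state the model examined here. It gives the random effects and the centring but no fixed effects and no contrast, and listing baseline among the responses is also what an equal-baseline model does. That stands: reading the arm effect at the centred time is an inference from the centring, and the point is conditional on it.

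Four stronger conclusions that a reader might draw are not supported:

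- *The model dilutes the treatment difference in general.* It does so at month 3. It is near unbiased at month 9 and overshoots with later centring.
- *Baseline adjustment alone lifts power from about half to about 90%.* That is true at month 3 only. At month 9 the like-for-like gain is small; most of the distance from there to the 85–94% available for an average through month 6 comes from choosing an earlier contrast, when more patients remain.
- *The straight line is fixed.* The plan allows nonlinear terms, and a post-treatment step with its arm interaction would remove the bias. Such terms are chosen after looking at the data and would not by themselves recover the precision.
- *A real difference is likely to be missed.* A baseline-adjusted ANCOVA with testing is planned, though only as an additional analysis.

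Retention is also uncertain. The figures of 16 and 29 need the added transplant hazard, while section 16.0 expects far fewer transplants in the first year. FACT-Hep is completed at the scan visit, so patients whose event is dated by that scan may still contribute.

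**Conclusion.** The concern holds in conditional form. As written, the main HRQL analysis has baseline as a response on a linear trend, states no adjustment or constraint, and leaves the tested contrast open. If the effect is the arm difference at the centred time, baseline adds almost no precision, and the estimate of a step difference moves with centring and attrition. The loss is large for an early contrast and modest at month 9. It is only 1–7% of z if the arms diverge linearly and the slope is tested. The SD, correlation, slope SD, effect and transplant hazard are all assumptions; only 98 per arm, the medians and the dropout rate come from the plan. The documents do not establish a general bias towards no difference. HRQL does not drive the sample size, so the trial's size and primary analysis are unaffected.

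**What to change.** In section 17.2.1, make the main HRQL analysis a mixed model for repeated measures. Either include baseline FACT-Hep as a covariate for post-baseline scores, or keep baseline as a response with arm means constrained equal there. Treat visit as a category with arm-by-visit terms. Prespecify one arm contrast averaged over the early post-treatment visits, for example through month 6; under the assumptions above, this contrast estimates 6.0 with SE 1.71–1.99 and power 85–94%. Keep the random-slope model as supportive, with its fixed effects, centring point and tested term written out. Say whether the same handling applies to the domain scores and to the other quantitative outcomes that section 17.2.3 refers to this approach.

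The cost is SAP wording; baseline FACT-Hep is already collected and no visit or sample size changes. The downsides are a few more parameters than a straight line, and a main contrast that describes the early period rather than the full 24 months.
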